**Nocturnal hypoglycemia:**

Nocturnal hypoglycemia is a hypoglycemia event (including severe hypoglycemia) that occurs at night and presumably during sleep.

**8.3.3.4. Nausea and Vomiting**

Nausea and vomiting events are considered AEs of interest and will be recorded as AEs in the CRF. For each event assessment of severity, duration and investigator's opinion of relatedness to the study drug and protocol procedure will be captured.

**8.3.3.5. Elevated Lipase or Amylase**

Serum amylase and lipase measurements will be collected as a part of the clinical laboratory testing at time points specified in the SoA (Section 1.3). Additional measurements may be performed at the investigator's discretion. Further diagnostic assessments will be recommended whenever lipase or amylase is confirmed to be  $\geq 3X$  ULN at any visit post randomization, even if the participant is asymptomatic (as per the algorithm refer for the monitoring of pancreatic events in Appendix 6, Section 10.6).

## 8.4. Pharmacokinetics

The characterization of the PK properties of tirzepatide in pediatric participants will be supported by collection of both predose and postdose PK blood samples per participant according to the SoA (Section 1.3).

At Visit 2 (Days 1 to 3), the sample is collected at 12 hours and 24 hours after the first dose during inpatient visit. At Visit 6 (Days 23 to 25), each participant will have PK sample collected at window of 24 to 96 hours post Day 22 dose. At Visit 9 (Days 41 and 42), each participant will have PK sample collected at window of 120 to 168 hours post Day 36 dose. For Visits 4, 8, and 11 (Days 15, 36, and 50), PK samples are collected prior to the intervention administration. Participants may be required to come to the site for PK-specific visits depending on sample window.

The actual date and time of the most recent SC injection administered prior to collecting the sample must be recorded. The actual date and time at which each sample was drawn must be recorded on the laboratory requisition form. Instructions for the collection and handling of blood samples will be provided by the sponsor.

The number and timing of PK samples are expected to be adequate in enabling comprehensive population PK and exposure-response modeling analyses within this special population.

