	
Comments: Tirzepatide injection sites must be rotated along the 4 abdominal quadrants. Dosing may be performed by clinic staff during in-clinic visits. Self-administration by participant or parent or legal guardian is permitted after the investigator assessed them as being adequately trained. The dose increase will happen at the 5th dose as indicated in Figure GPHV.1.1
														
Tirzepatide sampling for pharmacokinetics (hrs)		12, 24		P		X: within 24 to 96 hrs postdose		P	X: within 120 to 168 hrs postdose		P	X	X	X	
	
Comments: Sampling time is relative to the latest dosing time. The actual date and time of the sampling and the most recent SC injection administered prior to collecting the sample must be recorded. Days 15, 36 and final follow-up or early discontinuation sample must be time-matched with immunogenicity sampling. No sample collection is needed if the participant discontinued before receiving tirzepatide. P = predose samples that should be collected within an hour prior to dosing.
														
Immunogenicity sampling		P	P					P					X	X	
	
Comments: Exact time of sampling must be recorded. Days 15, 36 and final follow-up or early discontinuation sample must be time-matched with pharmacokinetic sampling. No sample collection is needed if the participant discontinued before receiving tirzepatide. P = predose samples that should be collected within an hour prior to dosing.
														

Abbreviations: BMI = body mass index; CRF = case report form; ECG = electrocardiogram; hrs = hour; IBT = intensive behavioral therapy; I/E = inclusion and exclusion criteria; P = predose.

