### **9.3.2. Pharmacokinetics**

#### **9.3.2.1. Pharmacokinetic Analyses**

All tirzepatide concentration data will be listed and summarized using descriptive analysis. Tirzepatide concentration may also be analyzed using a population PK approach via nonlinear mixed-effects modeling with the NONMEM® software to determine the  $C_{max}$  and  $AUC_{0-\tau}$  of tirzepatide by each dose and cohort.

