#### 10.2.1.1. Rationale for Blood Draws and Required Blood Volume

Careful consideration was given to collect the necessary information to address the key scientific objectives of this pediatric study while also minimizing invasive procedures and overall patient burden.

As PK profiling is a secondary objective of this study, the number of bioanalytical samples proposed is the minimum required to be able to derive a concentration-time profile for tirzepatide in children, based on an anticipated half-life of about 5 to 6 days. The blood volume for each PK sampling has been capped at 2 mL, which is the smallest volume of K3EDTA collection tube available.

Safety laboratory tests and BG had been limited to only the minimal number of samples to ensure safety of participants. The volume of blood required for safety clinical laboratory tests have been defined based on the analyte requirement in Appendix 2, which includes the monitoring of prepubertal hormones as part of pediatric monitoring.

The 10-mL blood volume for the immunogenicity sample is required to generate 5 to 7 mL serum divided into 6 aliquots due to the need to test for ADA and neutralizing antibodies using 4

aliquots (approximately 1 mL serum per aliquot) of serum in the event that the ADA sample is positive. A sample is required every 4 to 5 weeks, and another sample will also be drawn 2 weeks after initial treatment commencement to monitor IgM ADA as is often explicitly requested by FDA from experience.

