10.3 Pharmacokinetic Assessment

Pharmacokinetic analysis will be the responsibility of Lilly's PK/PD group. Tirzepatide concentration data will be analyzed using a population PK approach using nonlinear mixed-effects modelling techniques implemented on the NONMEM® software to determine the C_{max} and $AUC_{0-\tau}$ of tirzepatide by each cohort and dose.

Derivation of the PK parameters and TFL production will be the responsibility of Eli Lilly.

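### Does the lack of early PK samples after the dose increase undermine the raised-dose Cmax?

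*Protocol*

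**What the plan says.** The Schedule of Activities in the Protocol states: "The dose increase will happen at the 5th dose". With weekly injections from Day 1, the starting dose is given on Days 1, 8, 15 and 22 and the raised dose on Days 29, 36, 43 and 50.

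Protocol section 8.4 sets the sampling. Two draws follow the first dose, at 12 and 24 hours. Visit 6 has a "PK sample collected at window of 24 to 96 hours post Day 22 dose". At Visit 9, "each participant will have PK sample collected at window of 120 to 168 hours post Day 36 dose". The remaining on-treatment draws are troughs: "For Visits 4, 8, and 11 (Days 15, 36, and 50), PK samples are collected prior to the intervention administration". The Schedule of Activities adds Visit 12 (Day 57) and the follow-up visit. It also ties some draws to antibody sampling: "Days 15, 36 and final follow-up or early discontinuation sample must be time-matched with immunogenicity sampling". Visit 9 is not one of these.

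The secondary endpoints are AUC over the dosing interval and Cmax from a population PK model. Protocol section 9.3.2.1 wants them "of tirzepatide by each dose and cohort", and SAP section 10.3 "of tirzepatide by each cohort and dose". SAP section 10.3 gives this analysis to the sponsor's PK/PD group. Protocol section 9.3.2.2 excludes formal inference. Neither document specifies the absorption model.

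**The concern.** Read in order, the schedule has a visible gap. All samples drawn near a peak are on the starting dose, and all samples on the raised dose are late. Yet Cmax is to be reported for each dose. Raised-dose Cmax must therefore use an absorption rate learned on the starting dose, and the late samples can test that rate only weakly. If absorption were slower or faster at the higher dose, the reported Cmax would be biased and the data might not show it. An earlier Visit 9 draw would need no extra blood and no extra visit, so the omission looks easy to repair.

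**Working it through.** **1. The schedule.** Times are nominal, because the visit tolerances are blacked out.

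| Sample | Dose level | Hours since last injection |
|---|---|---|
| Visit 2, two draws | starting | 12 and 24 |
| Visit 4, Day 15 predose | starting | 168 |
| Visit 6 | starting | 24–96 |
| Visit 8, Day 36 predose | raised | 168 |
| Visit 9 | raised | 120–168 |
| Visit 11, Day 50 predose | raised | 168 |
| Visit 12, Day 57 | raised | 168 |
| Visit 13, 4–6 weeks after last dose | raised | 672–1008 |

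Count: 2+1+1+1+1+1+1+1 = 9 samples, and 9 × 2 mL = 18 mL. Both match the sampling summary in Protocol section 10.2.1. The gap is real as a matter of timing.

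**2. The model.** Protocol section 10.2.1.1 justifies the number of samples "based on an anticipated half-life of about 5 to 6 days". I take 5.5 days = 132 h, so ke = ln 2 / 132 = 0.00525 per h. The other inputs are assumptions:

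- one compartment with first-order absorption
- ka = 0.025, 0.05, 0.1 or 0.2 per h
- dose doubled at the fifth injection
- between-child SD of 30% for CL and V, and 50% for ka
- residual error 20%
- six children on tirzepatide
- Visit 6 draws at 24, 48, 72 and 96 h, and follow-up 35 days after the last dose

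Section 9.5 blacks out the sample size. The Synopsis prints 60 exposed in each of two weight categories. That makes 120 exposed, which does not fit its own total of 120 at a 1:1 ratio, so I do not rely on it.

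Concentration is the sum over injections i of D_i·ka / [V(ka − ke)] × (exp(−ke·s) − exp(−ka·s)), where s is the time since injection i. Single-dose Tmax = ln(ka/ke)/(ka − ke). For ka = 0.025 this is ln(4.76)/0.01975 = 79 h. The other three rates give 50, 31 and 19 h.

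**3. The stake if the assumption fails.** I changed ka from the fifth dose onward and fitted a model with one common ka to log concentrations. The table shows the error in the fitted raised-dose Cmax.

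| Tmax (h) | 79 | 50 | 31 | 19 |
|---|---|---|---|---|
| ka halved, current schedule | +10.6% | +12.5% | +9.6% | +6.1% |
| ka halved, Visit 9 at 24–96 h | +8.7% | +10.7% | +8.7% | +5.9% |
| ka doubled, current schedule | −11.4% | −8.9% | −5.9% | −3.7% |
| ka doubled, Visit 9 at 24–96 h | −10.0% | −8.2% | −5.8% | −3.7% |

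Retiming alone removes at most about 2 percentage points.

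**4. What retiming gains in precision.** These are standard errors of log Cmax from first-order Fisher information.

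| Tmax (h) | 79 | 50 | 31 | 19 |
|---|---|---|---|---|
| Common ka, either schedule | 0.108 | 0.103 | 0.099 | 0.097 |
| Separate raised-dose ka, prior SD 0.7 on the log shift, current | 0.133 | 0.131 | 0.120 | 0.107 |
| Same, retimed | 0.117 | 0.117 | 0.115 | 0.107 |
| Separate raised-dose ka, prior SD 0.3, current | 0.117 | 0.112 | 0.104 | 0.099 |
| Same, retimed | 0.113 | 0.109 | 0.103 | 0.099 |

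With a common ka, retiming gains nothing. With a separate ka and a modest prior, it gains less than 0.005. On the log scale, the halved-rate errors in step 3 are 0.101, 0.118, 0.092 and 0.059. Divided by the common-ka standard errors, they are 0.9, 1.1, 0.9 and 0.6 of one standard error.

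**5. Other cohorts.** Protocol section 6.1 supplies two prefilled strengths. Cohort 2's starting dose is prepared from one of them, with in-clinic dosing for Visits 2 to 5, and section 6.7 gives Cohort 2 its own overdose limit. The doses are blacked out, but this pattern suggests that Cohort 2's raised dose is the starting dose of Cohorts 1 and 3. That level would then have early samples from those cohorts, and only the top level would lack them. Pooling three cohorts of six with the 0.7 prior, and retiming Cohort 3 only, takes the top-level standard error from 0.082/0.085/0.082/0.071 to 0.074/0.077/0.078/0.071, a gain of at most 0.008.

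**The case for a change.** The best case for the concern has three parts.

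- **The assumption is unwritten and weakly testable.** Section 8.4 only expects the timing to be adequate. For 12 children, with lower variability than above (25% for CL and V, residual 15%) and bioavailability fixed, the chance of detecting a two-fold change in ka rises from 59% to 93% at ka 0.035 with an early Visit 9 window. At ka 0.07 it rises from 25% to 42%.
- **The gain is larger if bioavailability may also shift with dose.** In step 4 with the 0.7 prior, the standard error at Tmax 79 h would then fall from 0.194 to 0.127.
- **The draw is free to move.** It is not matched to antibody sampling, and three raised-dose troughs would remain.

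The timing facts stand, and so does the point that late samples test absorption weakly. The rest does not make a defect. The larger gains require a dose effect on absorption, or on bioavailability as well, that the documents give no reason to expect. At ka 0.15 the chance of detection is 9% on either schedule.

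Moving the window also has costs. It needs an amendment with ethics approval (Protocol section 10.1.1) and possibly re-consent (section 10.1.2). It would give a mixed schedule across children and leave no scheduled sample between 96 and 168 hours. The cohorts run in sequence, so some children may already have been sampled.

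A separate absorption term is a modelling choice for the sponsor's PK/PD group. The documents do not set out the absorption model, so its absence cannot be read as an omission from the plan.

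**Conclusion.** The concern does not hold. The schedule obtains absorption information on the starting dose and late-concentration information on the raised dose, and a population model can combine the two. With a common absorption rate there is no bias from this source, and moving Visit 9 does not change the precision of Cmax. The possible error of about 6–13% too high or 4–11% too low needs a two-fold change in rate that is purely hypothetical. It is small beside the up to 2-fold exposure difference by body weight that Protocol section 4.3 anticipates, and it concerns a descriptive endpoint.

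These sizes rest on the assumed one-compartment model, absorption rates, variability, dose ratio and number of children. That the plan is sound does not depend on the exact values. Whether to draw earlier at Visit 9, or to run a sensitivity model, is a preference on which competent pharmacometricians could differ.

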### 8.4.1. Bioanalysis

Samples will be analyzed at a laboratory approved by the sponsor and stored at a facility designated by the sponsor.

Concentrations of tirzepatide will be assayed using a validated liquid chromatography mass spectrometry method. The analyses of samples collected from placebo-treated participants are not planned.

Bioanalytical samples collected to measure study intervention concentrations will be retained for a maximum of 1 year following last participant visit for the study. During this time, samples remaining after the bioanalyses may be used for exploratory analyses such as metabolism, protein binding, or bioanalytical method cross-validation.

## 8.5. Pharmacodynamics

The PD exploratory analyses include treatment comparison based on the following variables:

- body weight
- BMI, and
- waist circumference.

### 8.5.1. Body Weight and Waist Circumference

Weight and waist circumference will be measured as indicated in the SoA (Section 1.3).

Wherever possible, the same scale will be used for all weight measurements throughout the study and the scale will not be moved or recalibrated.

Refer to Section 10.9 for guidance on the standardized protocols for weight and waist circumference measurements.

## **8.6. Genetics**

Genetics are not evaluated in this study.

## **8.7. Biomarkers**

Biomarkers are not evaluated in this study.

## **8.8. Immunogenicity Assessments**

At the visits and times specified in the SoA (Section 1.3), venous blood samples will be collected to determine antibody production against tirzepatide. Samples with detected tirzepatide ADA will be titered and evaluated for their ability to neutralize tirzepatide activity on the GIP and GLP-1 receptors. Antibodies may be further characterized for cross-reactive binding to native GIP and GLP-1 and, if such is detected, then for cross-reactive neutralizing antibodies against native GIP and GLP-1. To interpret the results of immunogenicity, a venous blood sample will be collected at the same time points after predose visit (Day 1) to determine the serum concentrations of tirzepatide. Detailed instructions for the sample collections and handling will be provided by the sponsor. Immunogenicity will be assessed by a validated assay designed to detect ADAs in the presence of tirzepatide at a laboratory approved by the sponsor.

Treatment-emergent ADAs (TE ADA) are defined in Section 9.3.4.

If the immunogenicity sample at the last scheduled assessment or discontinuation visit indicates TE ADA, the sponsor may request for additional samples to be taken until the signal returns to baseline (that is, no longer indicates TE ADA) or for up to 1 year after last dose, as a part of safety measures. The requirement for possible additional, unscheduled ADA safety follow-up must be included in the ICF.

Refer to Appendix 1 (Section 10.1.9) for details on sample retention.

## **8.9. Health Economics**

Health economics or medical resource utilization and health economics parameters are not evaluated in this study.

## 9. Statistical Considerations

The statistical analysis plan will be finalized prior to database lock, and it will include a more technical and detailed description of the statistical analyses described in this section. This section is a summary of the planned statistical analyses of the most important endpoints, including primary and key secondary endpoints.

### 9.1. Statistical Hypotheses

Not applicable.

#### 9.1.1. Multiplicity Adjustment

Not applicable. No formal statistical analysis will be performed.

### 9.2. Analyses Sets

For the purposes of analysis, the following analysis sets are defined:

Participant Analysis Set	Description
Full analysis set	All enrolled participants. Participants will be included in the analyses according to the planned intervention.
Safety analysis set	All participants who are exposed to study intervention. Participants will be analyzed according to the intervention they actually received.

The full analysis set will be used to summarize disposition and demographic characteristics.

The safety analysis set will be used for safety evaluation.

### 9.3. Statistical Analyses

#### 9.3.1. General Considerations

Statistical analysis of this study will be the responsibility of the sponsor or its designee.

PK analyses will be conducted on data from all participants who receive at least 1 dose of the study intervention and have evaluable PK.

Safety analyses will be conducted for all enrolled participants who were administered study intervention, whether or not they completed all protocol requirements.

A detailed description of participant disposition will be provided at the end of the study. All participants who discontinue from the study will be identified, and the extent of their participation in the study will be reported. If known, a reason for their discontinuation will be given.

The demographic characteristics of enrolled participants (including but not limited to age, sex, and race) will be summarized. Additional exploratory analyses of the data will be conducted as deemed appropriate.

### **9.3.2. Pharmacokinetics**

#### **9.3.2.1. Pharmacokinetic Analyses**

All tirzepatide concentration data will be listed and summarized using descriptive analysis. Tirzepatide concentration may also be analyzed using a population PK approach via nonlinear mixed-effects modeling with the NONMEM® software to determine the  $C_{max}$  and  $AUC_{0-\tau}$  of tirzepatide by each dose and cohort.

#### **9.3.2.2. Pharmacokinetic Statistical Inference**

No formal statistical analysis will be performed.

### **9.3.3. Safety Analyses**

#### **9.3.3.1. Clinical Evaluation of Safety**

All study intervention and protocol procedure AEs will be listed, and if the frequency of events allows, safety data will be summarized using descriptive methodology.

The incidence of AEs will be presented by severity and by association with study intervention as perceived by the investigator. AEs reported to occur prior to enrollment will be distinguished from those reported as new or increased in severity during the study. Each AE will be classified by the most suitable term from the medical regulatory dictionary.

The number of study intervention-related SAEs will be reported.

#### **9.3.3.2. Statistical Evaluation of Safety**

Safety parameters that will be assessed include safety laboratory parameters, vital signs (including blood pressure and pulse rate), body weight and BMI, and ECG parameters.

Continuous safety variables will be summarized using descriptive statistics. Categorical safety variables will be summarized using count and percentage.

Additional analysis will be performed if warranted upon review of the data.

### **9.3.4. Evaluation of Immunogenicity**

The frequency and percentage of participants with preexisting ADAs, ADAs at any time postbaseline, and TE ADA+ to tirzepatide may be tabulated. TE ADAs are defined as those with a titer 2-fold (1 dilution) greater than the minimum required dilution (1:10) of the ADA assay if no ADAs were detected at baseline (treatment-induced ADA) or those with a 4-fold (2 dilutions) increase in titer compared to baseline if ADAs were detected at baseline (treatment-boosted ADA). For the TE ADA+ participants, the distribution of maximum titers may be described. The frequency of neutralizing antibodies, if assessed, and cross-reactivity to native GIP and GLP-1 may also be tabulated in TE ADA+ participants.

The relationship between the presence of antibodies and the PK parameters and PD response, including safety and efficacy to tirzepatide, may be assessed.

## 9.4. Interim Analysis

No interim analyses are planned for this study. If an unplanned interim analysis is deemed necessary for reasons other than a safety concern, the protocol must be amended.

For further information on the review of safety and tolerability data during the study, refer to Section [6.5.1](#).

## 9.5. Sample Size Determination

Approximately ~~CC1~~ participants may be enrolled. This will allow PK characterization in at least ~~C~~ participants each, exposed to tirzepatide, for the weight categories <50 kg and  $\geq$ 50 kg, respectively. Evaluable participants are participants who receive at least 1 dose of the study intervention and have at least 1 evaluable PK sample. The sample size is customary for Phase 1 studies evaluating safety, tolerability, and PK, and is not powered on the basis of any a priori statistical hypothesis testing for efficacy.

Participants who do not complete all the study procedures may be replaced to achieve the planned number of completers.

**Note:** Enrolled means a participant's parent or their legally acceptable representative's, agreement to participate in a clinical study following the completion of the informed consent process and assent where applicable and screening. Potential participants who are screened for the purpose of determining eligibility for the study, but do not participate in the study, are not considered enrolled. A participant will be considered as enrolled if the informed consent is not withdrawn prior to participating in any study activity after the screening visit.

## 10. Supporting Documentation and Operational Considerations

### 10.1. Appendix 1: Regulatory, Ethical, and Study Oversight Considerations

#### 10.1.1. Regulatory and Ethical Considerations

This study will be conducted in accordance with the protocol and with the following:

- consensus ethical principles derived from international guidelines including the Declaration of Helsinki and Council for International Organizations of Medical Sciences (CIOMS) International Ethical Guidelines
- applicable International Council for Harmonization of Technical Requirements for Pharmaceuticals for Human Use (ICH) GCP Guidelines, and
- applicable laws and regulations.

The protocol, protocol amendments, ICF, applicable assent forms, Investigator Brochure, and other relevant documents (for example, advertisements) must be submitted to an IRB/IEC by the investigator and reviewed and approved by the IRB/IEC before the study is initiated.

Any amendments to the protocol will require IRB/IEC approval before implementation of changes made to the study design, except for changes necessary to eliminate an immediate hazard to study participants.

Protocols and any substantial amendments to the protocol will require health authority approval prior to initiation except for changes necessary to eliminate an immediate hazard to study participants.

The investigator will be responsible for the following:

- providing written summaries of the status of the study to the IRB/IEC annually or more frequently in accordance with the requirements, policies, and procedures established by the IRB/IEC
- notifying the IRB/IEC of SAEs or other significant safety findings as required by IRB/IEC procedures, and
- providing oversight of study conduct for participants under their responsibility and adherence to requirements of 21 Code of Federal Regulations (CFR), ICH guidelines, the IRB/IEC, European regulation 536/2014 for clinical studies (if applicable), and all other applicable local regulations.

Investigator sites are compensated for participation in the study as detailed in the clinical trial agreement.

